 capsule at night for the first 2 weeks, and then two capsules of the placebo at night for
 the remaining 4 weeks.

Blinding

This study will include a placebo. Study participants and providers will be blinded to which treatment they are receiving (placebo or LDN). Keefer's Compounding Pharmacy will create a placebo and compound the study medication into a 2 mg dose capsule. The NorthShore pharmacy will then place 70 capsules of placebo or study medication in moisture tight, light-resistant prescription bottles with appropriate labeling. When a participant enrolls, the pharmacy will provide the prescription bottle with the correct pills (either placebo or study medication) for the research personnel to pick up from the NorthShore pharmacy and give to the participant. This will ensure the trial remains double-blinded.

Randomization

The randomization will be done by statistician prior to initiation of the study, and will be kept with the pharmacy. Once a participant is enrolled, a call will be made to the pharmacy who will supply the correct medication, either the LDN or placebo, to maintain blinding.

Indication and patient population

LDN has demonstrated amelioration of symptoms in conditions associated with interstitial/painful bladder syndrome. The proposed mechanism of action of LDN in animal studies suggests that neuroinflammation is reduced, opioid signaling is upregulated thus increasing the sensitivity of signaling, and endogenous opioids are increased, including beta-endorphins, which have anti-inflammatory properties and may produce neuropsychological benefits. IC/PBS is a poorly understood syndrome, characterized by pain and likely inflammation with several treatment modalities that are either not effective, time consuming or have adverse risks associated with them.

Sample Size:

Using a randomized double-blinded design, we estimate that a sample size of 22 patients in each group (total N=44) will achieve an 80% statistical power to detect a minimum 30% reduction in pain symptoms for LDN over placebo group when using an alpha of 0.05.

Duration and Number of Sites

Enrollment will begin following approval by the IRB in the spring of 2020, and patient participation will last for six weeks. Patients diagnosed with IC/PBS by urogynecology providers at the Center for Pelvic Health in the NorthShore University HealthSystem will be eligible to participate.

Study Population

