Patients diagnosed with IC/PBS by one of the urogynecology providers at the Center for Pelvic Health in the NorhShore University HealthSystem by diagnostic criteria for IC/PBS by AUA guidelines will be eligible to participate. A patient must then meet all applicable inclusion and exclusion criteria.

Inclusion criteria

- 1. Patients aged eighteen and older
- 2. Meet criteria for IC/PBS as defined by the American Urology Association as "an unpleasant sensation (pain, pressure, discomfort) perceived to be related to the urinary bladder, associated with lower urinary tract symptoms or more than six weeks duration, in the absence of infection or other identifiable causes" (8)

- 3. Newly diagnosed and treatment naïve for IC/PBS or previously diagnosed with IC/PBS, but who have no received treatment in the past four weeks. Patient who use anti-inflammatory medication on an as needed basis in the four weeks prior to the study will be included.
- 4. Have had a cystoscopy in the last 6 months prior to study entry to rule out confounding conditions
- 5. English speaking
- 6. Working telephone number
- 7. Able to attend research visits

Exclusion criteria:

- 1. Patients under the age of 18
- 2. Patients with known liver disease, including total bilirubin >1.2, AST> 32, ALT> 54 within the last six months or with enrollment screening testing
- 3. Patients with known kidney disease
- 4. Patients who have thyroid disease and who are taking thyroid replacement medications
- 5. Patients with known neurologic disease affecting bladder function
- 6. Patients with known bladder or urethral cancer
- 7. Patients with bladder, urethral, or ureteral calculi
- 8. Patients who have had a positive urine culture or a clinical UTI in the past 6 weeks
- 9. Patients who are currently pregnant or breast feeding (15)
- 10. Patients who are actively using opioid analgesics
- 11. Patients with moderate-severe alcohol use disorder
- 12. Patients who are actively using sleep aids
- 13. Patients who are regularly using anti-inflammatory medications, such as daily Celebrex for arthritis. Those who use an anti-inflammatory medication on an as needed basis may use the medication prior to enrollment in the study.
- 14. Patients who have had a known adverse reaction to naltrexone
- 15. Patients who are acutely ill
- 16. Patients who are diagnosed with a significant psychological comorbidity that would interfere with study participation (32)

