- 17. Patients who have had a bladder instillation or had oral medical treatment for IC/PBS in the past four weeks.
- 18. Patients diagnosed with other chronic pelvic pain syndromes, such as endometriosis
- 19. Patients who are unable to swallow pills/capsules
- 20. Patients who have had previous treatment with low-dose naltrexone
- 21. Patients who have previously scheduled surgeries or procedure during the study time period that would require analgesia.
- 22. Patients who are sexually active and of childbearing potential who are unwilling to use an established and reliable form of contraception for the duration of the study.
- 23. Patients who are unwilling to have a serum blood test to assess serum transaminases and serum bilirubin.

Withdrawal criteria:

Patients can self-withdrawal at any time from this study, and they will be informed that doing so will have no impact on their medical care within the practice. Patients who become pregnant, experience serious adverse effects, or are deemed unable to continue the study for by study personnel will be withdrawn by study personnel. In the

event of withdrawal from the study, the participant will be asked to return any unused study medication.

Human Subject Protection Rationale for Subject Selection

Patients meeting criteria by the American Urology Association definition of IC/PBS are the ideal study population to investigate a novel therapy for IC/PBS.

Evaluation of benefits, risks and discomforts

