Patients will be introduced to the study in a few different ways. The provider may mention the study and supply the consent form; the provider may mention the study, or if study personnel is available and the patient's schedule allows, study personnel will meet with the potential participant in person. At that time, they will be asked about inclusion and exclusion criteria and be given a consent form, if they are interested. For patients not seen by study personnel at the time of their appointment, they will be contacted by phone by research personnel. Any patient declining participation will be noted, so as not to contact them about this study again.

Potential participants will be encouraged to read the consent form thoroughly and to discuss the study with family, a primary care physician, other physicians, and/or friends. If they desire to participate, they will make an appointment to return to the Center for Pelvic Health of the NorthShore University HealthSystem to sign the consent form, to complete intake forms, to have their blood drawn, and to receive the study medication.

Compensation

Study participants will receive \$50 gift card upon completion of the study if they finish all study questionnaires, blood work, vital sign assessments, and the two bladder diaries. This will be given to them in person at their follow up appointment or mailed to them once all materials are completed. In the event that study participants are unable to complete the study, they will receive prorated compensation of \$20 in the form of a gift card.

Schedule of visits/assessments

Screening/eligibility determination

Patients must first receive a clinical diagnosis of IC/PBS by one of the urogynecology providers at the Center for Pelvic Health in the NorhShore University HealthSystem. As this patient population is difficult to identify based on chief complaint, potential study participants will be recruited after diagnosis of IC/PBS. Patients interested in participating will be screened by research personnel, either in person, or over the telephone. Only patients meeting all relevant inclusion criteria, and those who do not meet the exclusion criteria will be able to participate. These individuals will be given the consent form, either in person or through the mail.

Consent

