Consent will be obtained in clinic by research personnel, after study participants have had ample time to discuss the study with family, a primary care physician, other physicians, and/or friends. They will make an appointment with research personnel at a convenient time for the study participant.

Enrollment

After signing the consent form, participants will be given a study identification number (ID). This ID will not be linked to their medical record. There will be a master sheet kept in a locked filing cabinet at the Center for Pelvic Health at the Skokie Ambulatory Care Center. Only those study personnel on the R8.1 delegation log will be able to access this master sheet. The participant's name and study ID will also be typed into a spreadsheet and stored on the Collaboration Portal, and access will only be given to [name].

Baseline Evaluation

Study participants will be asked to answer demographic information including:

- 1. Age
- 2. BMI
- 3. Menopausal status
 - a. If premenopausal, type of contraception
- 4. Tobacco use
- 5. Marijuana use
- 6. Pain medication use in the last month
- 7. Prior medical and surgical history, including medications and allergies
- 8. Length of time they have been experiencing symptoms of IC/PBS
- 9. Specific symptoms they are experiencing

Along with the following validated questionnaires:

- 1. Interstitial Cystitis Symptom Index
- 2. Interstitial Cystitis Problem Index
- 3. Pelvic pain and urgency/frequency patient symptom scale (PUF)
- 4. Visual Analog Scale
- 5. Medical Outcomes Study Short Form 36 (SF-36)
 - a. This will be scored prior to the participant leaving the office. In the event that they have low scores in areas assessing "role limitations due to emotional problems," (questions 17, 18, 19) "energy/fatigue" (23, 27, 29, 31) or "emotional well being" (24, 25, 26, 28, 30), participants will be offered a referral to discuss any mental health concerns, if they desire.

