At the enrollment appointment, vital signs will be obtained, including blood pressure. If participants are premenopausal, they will be asked to undergo a urine pregnancy test. Patients will be given a lab requisition form for a hepatic panel at the time of enrollment for a blood draw to evaluate serum transaminases and bilirubin. Once participants have their blood draw, they will be given and instructed to take one capsule nightly for two weeks, then increase their dosage to two capsules at night for four weeks. They will be given a log where they can record the date and time they take the medication, along with space for any additional notes they wish to share. Prior to starting the study medication, patients will be asked to complete a 24-hour bladder diary. They will also be instructed not to start the study medication until their blood work results with normal liver function. Participants will be called with the results of their blood work.

Treatment Schedule

Participants will be given a prescription bottle with 70 capsules. For the first two weeks, participants will take 1 capsule at night. After two weeks, they will take two capsules at night. Participants will be given a log to record taking the medication.

All patients will receive information about a bladder diet and bladder drills to assure patients are receiving treatment known to be beneficial in IC/PBS.

Follow-up Schedule

If serum transaminases and bilirubin are elevated at the baseline blood test, study participants will be notified of their results, withdrawn from the study, and encouraged to follow up with their primary care provider.

After two weeks, participants will be contacted by research personnel to check to see that they completed the bladder diary, to make sure they are taking the medication, and to ask about any adverse effects from the study medication. If adverse effects are noted, study personnel will attempt to trouble shoot. For example, the most commonly reported adverse effect in previous trials is vivid dreams. If study participants experience this, they will be encouraged to try taking the medication in the morning. If study participants have not completed the 24 bladder diary, they will be encouraged to do so as soon as possible.

Participants will also be encouraged to call prior to this two week check in telephone call with any questions or concerns that arise.

At the completion of the six weeks, patients will return to the office for:

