
Patients who have been newly diagnosed with IC/PBS or those who have not received treatment in the past four weeks, who are interested in participating in the study and who meet inclusion, and who do not meet exclusion criteria will be given a consent form in the clinic or sent one by mail. Potential participants will be encouraged to discuss the study with family, a primary care physician, other physicians, and/or friends.

Once patients decide they would like to participate, they will make an appointment to return to the Center for Pelvic Health of the NorthShore University HealthSystem and meet with research personnel for:

- 1. Consent
- 2. Vital sign assessment including blood pressure
- 3. Completion of intake forms

- 4. Randomization
- 5. Blood collection
- 6. Urine pregnancy test if premenopausal
- 7. Distribution of study medication.
- 8. All patients will receive information about a bladder diet and bladder drills to assure patients are receiving treatment known to be beneficial in IC/PBS.

Prior to starting the study medication, patients will be asked to complete a 24-hour bladder diary.

The study medications will be listed in epic as "naltrexone/placebo" to inform other providers that the patient may be taking low-dose naltrexone as part of a research study. The study medication and placebo will be free of charge to patients, placing no additional financial burden on the patient or insurance company. The blood collection and hepatic panel will also be performed free of charge for study participants.

Participants will also be encouraged to contact research personnel with any questions or concerns at any point during the research study. If serum transaminases and bilirubin are elevated at the baseline blood test, study participants will be notified of their results, withdrawn from the study, and encouraged to follow up with their primary care provider.

Participants will be instructed to take one capsule nightly for two weeks, then increase their dosage to two capsules at night for four weeks. They will be given a log where they can record the date and time they take the medication.

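### Allocation and bottle hand-over come before the liver result that decides eligibility, and no week-6 outcome collection is described for people withdrawn from the study, although the analysis is stated to be ITT

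*Combined protocol and SAP*

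**What the plan says.** Order of events. Under Randomization, the trigger for allocation is enrolment: "Once a participant is enrolled, a call will be made to the pharmacy who will supply the correct medication". No condition on a laboratory result is attached. Under Consent and assent process and documents, participants return for one appointment "to sign the consent form, to complete intake forms, to have their blood drawn, and to receive the study medication". The numbered list under Study procedures puts randomization at item 4, blood collection at item 5, the pregnancy test ("Urine pregnancy test if premenopausal") at item 6 and distribution of study medication at item 7. Baseline Evaluation hands over the capsules once blood has been drawn and adds: "They will also be instructed not to start the study medication until their blood work results with normal liver function".

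Eligibility. Exclusion criterion 2 covers "Patients with known liver disease, including total bilirubin >1.2, AST> 32, ALT> 54 within the last six months or with enrollment screening testing", so the enrolment panel itself decides eligibility. Follow-up Schedule and Study procedures both deal with an abnormal result by withdrawal: "If serum transaminases and bilirubin are elevated at the baseline blood test, study participants will be notified of their results, withdrawn from the study".

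After withdrawal. Withdrawal criteria state that in the "event of withdrawal from the study, the participant will be asked to return any unused study medication". The sections on early withdrawal add that the reason is documented and that compensation is prorated. None of them mentions questionnaires or a week-6 contact.

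Measurement and analysis. The ICSI and the VAS are completed at baseline and at the six-week visit; the two-week telephone call collects neither. Data Analysis states intention to treat and a linear mixed model with a patient-specific random intercept. It does not define the ITT set and states no missing-data rule or sensitivity analysis.

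**The concern.** There are two routes by which a randomised person ends with no post-baseline primary outcome.

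(A) Someone who fails the enrolment liver panel is already randomised and holds a bottle when the result arrives, and is then removed. An ITT analysis of everyone randomised would include this person, who was never eligible and never dosed. The plan does not say how such people are counted. Their bottle and their place in the allocation list are also used up.

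(B) Someone withdrawn from the study after starting drug but before week 6 has baseline values only. With a single post-baseline assessment, no intermediate measurement can stand in. If withdrawal were related to arm and to outcome, the efficacy comparison could be distorted, and week-6 data that were not collected cannot be recovered later.

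**Working it through.** **Order of events.** The conclusion does not rest on the numbered list alone. Allocation is triggered at enrolment (Randomization). Blood draw and receipt of medication fall at the same appointment (Consent and assent process and documents). An instruction to wait for the result (Baseline Evaluation) is needed only if the bottle is already in hand. The three sections agree that hand-over precedes the result. The pregnancy test is a weaker case: it follows randomization only in the list order, and it precedes distribution.

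**Supply.** A course is 14 x 1 + 28 x 2 = 70 capsules. Drug packaging orders 1,540 capsules, and 1,540 / 70 = 22 courses. Read as 1,540 of each product, this is 22 bottles per arm with no stated spare.

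**The plan's power figure.** Sample Size gives 22 per group, 80% power and alpha 0.05 for a 30% reduction, but no SD, placebo rate or sidedness. The figure cannot be reproduced, only back-solved. For a two-sided, two-sample t-test at 0.05 with n = 22 per arm and power 0.80, the implied standardised effect is d = 0.865. All power figures below take that as given.

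**(A) Liver-test failures.** The failure rate p is not in the documents; 2%, 5% and 10% are assumptions. Expected failures are 44p, the chance of at least one is 1 - (1 - p)^44, and evaluable people per arm are 22(1 - p).

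| p (assumed) | Expected failures | P(at least one) | Per arm | Power |
|---|---|---|---|---|
| 2% | 0.88 | 59% | 21.56 | 79% |
| 5% | 2.2 | 90% | 20.9 | 78% |
| 10% | 4.4 | 99% | 19.8 | 76% |

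Removal happens before dosing and does not depend on arm, so the loss is of numbers and balance, with no bias expected.

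**(B) Withdrawal before week 6.** The background summary of earlier studies reports that 5 of 40 people (12.5%) left a six-month LDN pilot in multiple sclerosis. The disease and duration differ, the reasons are mixed and there is no comparator, so this is only an anchor. If 12.5% are lost in both arms, 22 x 0.875 = 19.25 remain per arm and power is 74%. If they are lost in one arm only (22 versus 19.25), power is 77%.

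The mixed model can keep a baseline-only record, but gains little from it. If 4 of 22 per arm lack week 6, the standard error of the treatment-by-time term rises by 7% to 9% for a within-patient correlation of 0.3 to 0.7. Dropping those people raises it by sqrt(22/18) - 1 = 10.6%.

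**Possible bias, illustration only.** If a share w of one arm is missing and would have differed from those retained by D SD, the retained mean is off by w x D.

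- 0.05 x 0.25 = 0.0125 SD, or 0.0125 / 0.865 = 1% of the assumed effect.
- 0.125 x 0.5 = 0.0625 SD, or 7%.
- 0.125 x 1.0 = 0.125 SD, or 14%.

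Here w and D are assumed. D should be the difference left after the model has used the baseline value, so with raw differences these figures are an upper range.

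**The case against.** On (A), the harm is minor. Exclusion 2 also covers results from the last six months, and eligibility is screened before the consent visit, so some abnormal cases will never be randomised. The failure rates above are assumptions. All of this stands, and it limits the size of the problem. It does not change the order of events, because pre-screening cannot supply a result from blood not yet drawn. One could instead predefine the exclusion of never-dosed ineligible people on pre-dose data. That would settle the analysis set but not the lost bottle.

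On (B), the gap is inferred from silence: no section forbids outcome collection after withdrawal, and some appendices are not reproduced in the text reviewed. The tolerability survey is given at the follow-up visit and asks about stopping the medication, so the plan appears to expect some people who stopped drug to attend week 6, when the ICSI and VAS are completed. This stands, and the gap is confined to people withdrawn from the study.

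A reader might infer that LDN will cause unequal withdrawal, because the fibromyalgia crossover study reported vivid dreams (37%) and headache as more marked on LDN. The documents do not support that step: those are adverse-effect reports, not withdrawals, and the protocol has its own handling for vivid dreams. A reader might also infer that the provision on withdrawing people who return many capsules removes efficacy data. Scheduled capsule return is at the visit where the questionnaires are completed, and no section orders collected data to be discarded.

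**Conclusion.** Part A holds on the text. The plan as written randomises some people whose eligibility is unsettled and removes those who fail before dosing. The consequences are an undefined ITT set, bottles lost from an exact supply, and a fall in power from 80% to between 79% and 76% under assumed failure rates of 2% to 10%. Bias is not expected.

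Part B holds in a narrow form and with less certainty. No week-6 collection is described for people withdrawn from the study, so the efficacy comparison would rest on missing at random, with no sensitivity analysis stated. The number affected and any imbalance by arm are unknown. The 74% to 77% power figures and the 1% to 14% bias range are illustrations, the latter an upper range. Every power figure depends on the back-solved d of 0.865.

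Both parts should be fixed; neither shows that the trial's result would be invalid.

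**What to change.** (1) Reconcile Randomization, Consent and assent process and documents, Enrollment, Baseline Evaluation and Study procedures so that the pharmacy call and bottle release follow the liver-panel and pregnancy-test results. Count those who fail as screen failures, not as randomised. The cost is a second contact or delivery for the bottle, although participants already wait for the result and are called with it. A few more people must also be consented to randomise 44: 44/0.98, 44/0.95 and 44/0.90 give 45, 47 and 49 after rounding up, at the assumed failure rates.

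(2) In Data Analysis, define the ITT set as all randomised participants. In the withdrawal sections, state that the week-6 ICSI and VAS will be sought by mail or telephone from anyone withdrawn from the study, unless they withdraw consent. Add a simple sensitivity analysis to missing at random, for example shifting the imputed week-6 values of withdrawn participants over a stated range, separately by arm. The cost is a little staff time and a few lines in the analysis section.

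Both changes need a protocol amendment. Neither alters when study drug is stopped.

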- A provider appointment to discuss additional therapeutic options for treatment of IC/PBS
- 2. Vital sign assessment including blood pressure
 - a. If blood pressure is elevated from baseline, will recommend patients repeat a blood pressure with the primary care provider; if they do not have a primary care provider, we will have them obtain a blood pressure check in 1 week.
- 3. Blood draw for study exit hepatic panel
 - a. Study participants will be called with the results of their post-study blood test results
- 4. Complete study questionnaires
 - a. Interstitial Cystitis Symptom Index

- b. Interstitial Cystitis Problem Index
- c. Pelvic pain and urgency/frequency patient symptom scale (PUF)
- d. Visual Analog Scale
- e. Medical Outcomes Study Short Form 36 (SF-36)
 - i. This will be scored prior to the participant leaving the office. In the event that they have low scores in areas assessing "role limitations due to emotional problems," (questions 17, 18, 19) "energy/fatigue" (23, 27, 29, 31) or "emotional wellbeing" (24, 25, 26, 28, 30), participants will be offered a referral to discuss any mental health concerns, if they desire.
- f. Study completion and tolerability survey
- 5. Return unused study medication
- 6. Provide two completed 24-hour bladder diaries
 - a. One performed prior to starting the medication
 - b. One performed at completion of the study last day
 - c. Participants will be given instructions about completing this on the last day of taking study medication, or the day after completion of all study.

Ethical and Regulatory considerations Regulatory document collection:

Patients will fill out the above mentioned forms prior to starting the study, then again at the conclusion of the study. Documents will be kept in a locked filling cabinet and only those individuals listed on the RI 8.1 delegation log will be able to access it. In addition, the information will be typed into spreadsheets and stored on the Collaboration Portal.

IRB review

IRB approval of the revised protocol including the comments and recommendation from the FDA will be submitted for review prior to initiation of enrollment.

Informed consent administration:

Potential study participants will be given the consent form to participate in this study prior to being asked to formally enroll by signing the consent form to allow for ample time to read the consent form and to discuss the study with family, other physicians and friends, if they so choose.

Study procedures

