Adverse Experiences (AEs): Study participants will be asked to document any adverse experiences or events they experience while participating in the study. The National Cancer Institute Common Terminology Criteria for Adverse Events (CTCAE) version 5.0 will be used for adverse event reporting. The CTCAE describes an adverse event as "any unfavorable and unintended sign, symptom, or disease temporally associated with the use of a medical treatment or procedure that may or may not be considered related to the medical treatment or procedure."

Documentation of AEs: All AEs experienced by study participants will be documented in the collaboration portal.

Coding of AEs: AEs will be given a grade according to the CTCAE version 5.0

Serious Adverse Events

Definition: Serious AEs will be given a grade according to the CTCAE version 5.0

Reporting: Serious AEs will be documented in writing

Expected AEs/toxicities: To date, there are no reports of interactions between LDN and other medications. The sample size of these studies is small, and there are likely a large number of interactions that have yet to be tested (39). Other trials have reported vivid dreams (34), nausea, epigastric pain, mood alteration, mild irritability, headache, and joint pain. (43)

Unplanned visits: Study participants will be encouraged to contact research personnel with any questions or concerns they have about the medication or the study. If study personnel determine the patient needs a clinic visit, the patient will be seen by a provider, and that visit will be documented in Epic as a medical visit. The visit will also be included in the patient's research documentation.

Subject Completion and Early Withdrawal Procedures for completion

Upon completion of the six-week study period, participants will have an appointment with their physician to discuss additional treatment options for IC/PBS. At that visit, study participants will complete study forms and submit two 24-hour bladder diaries, and have a blood sample collected. They will receive \$50 in compensation. In the event that study participants are unable to complete the study, they will receive a prorated compensation of \$20 in the form of a gift card.

Procedures for early withdrawals:

Patients will be free to withdrawal for any reason or if deemed necessary by research staff or any other medical provider.

Reasons for withdrawals:

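### The pre-treatment bladder diary is collected only at week 6: leavers lose their void data, and a diary completed on treatment can be filed as baseline

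*Combined protocol and SAP*

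**What the plan says.** **Purpose of the diary.** Secondary outcomes b and c (Outcome measures) are the changes in day and night voids between a 24-hour diary kept before treatment and one kept at the end of six weeks.

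**When the first diary is due.** Baseline Evaluation and Study procedures both state: "Prior to starting the study medication, patients will be asked to complete a 24-hour bladder diary". It is a home task after enrollment. Under Baseline Evaluation, capsules are supplied once blood has been drawn, and participants are told to wait for a normal liver result, which is given by telephone.

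**When it is handed in.** The week-6 lists under Follow-up Schedule and Study procedures include "Provide two completed 24-hour bladder diaries". Procedures for completion agrees: "At that visit, study participants will complete study forms and submit two 24-hour bladder diaries, and have a blood sample collected". No earlier hand-in is described.

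**The only earlier check.** Under Follow-up Schedule, after two weeks participants are "contacted by research personnel to check to see that they completed the bladder diary". Then: "If study participants have not completed the 24 bladder diary, they will be encouraged to do so as soon as possible". Study procedures repeats this and specifies a phone contact.

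**Withdrawal.** Under Withdrawal criteria, "the participant will be asked to return any unused study medication". Neither the withdrawal text nor the reasons for withdrawal mention the diary or an early-termination visit.

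**Payment.** The full $50 is due "if they finish all study questionnaires, blood work, vital sign assessments, and the two bladder diaries". Those who cannot complete the study receive $20, which is not tied to a diary.

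**Analysis.** Efficacy analyses specifies intention-to-treat with a mixed model containing treatment, time and their interaction. No missing-data rule is given.

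**The concern.** A change score depends on its baseline. The ICSI and VAS baselines are completed at the enrollment visit and stay on file whatever happens later. The void baseline stays with the participant for the whole treatment period, which creates two problems.

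- **Loss.** A participant who leaves and never attends week 6 contributes no void observation. The intention-to-treat mixed model has nothing to use for that person, and the baseline voids of dropouts cannot be compared with those of completers. Some exits are built into the plan: Study procedures lists randomization before blood collection, and participants with elevated liver results are then withdrawn.
- **Validity.** A diary completed at week 2 describes a participant who should by then have taken capsules for two weeks. If it is filed as baseline, any effect already present is subtracted from the measured change.

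**Working it through.** **1. The passages side by side**

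| Step | Is the first diary seen or collected by staff? |
|---|---|
| Enrollment visit | No; completed afterwards at home |
| Liver-result call | No; the plan mentions only the blood result |
| Two-week contact | No; the participant is asked whether it was done |
| Withdrawal | No; capsules only |
| Week-6 visit | Yes; both diaries together |

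The diary mentioned at two weeks can only be the pre-treatment one, because the exit diary is not due until the last day of medication or the day after. The same contact checks that the participant is taking the medication. The instruction to complete a missing diary does not distinguish those who have started capsules from those who have not. It therefore permits what the pre-treatment requirement rules out.

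**2. Dilution from late baseline diaries**

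The plan gives no figures for this, so both inputs are assumptions: q is the share of baseline diaries actually kept at week 2, equal in both arms, and f is the share of the week-6 void effect already present at week 2.

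Expected difference retained = 1 − q × f

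| q | f = 0.25 | f = 0.50 | f = 0.75 |
|---|---|---|---|
| 0.10 | 97.5% | 95.0% | 92.5% |
| 0.25 | 93.75% | 87.5% | 81.25% |
| 0.50 | 87.5% | 75.0% | 62.5% |

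For example, 1 − 0.50 × 0.75 = 0.625.

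**3. Power recovered by collecting the diary early**

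The plan has no sample-size figure for voids to reproduce. Its 22 per group is sized on pain, without an SD, responder rates or a dropout allowance. The assumptions here are a void effect with 80% power (two-sided 0.05) if all 44 participants have both diaries; a fraction d with no week-6 diary; and correlation ρ between visits. In a two-visit random-intercept model, the variance of the treatment-by-time term relative to complete data is:

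- both diaries lost: R = 1/(1 − d)
- baseline diary kept: R = [(1 + ρ)/(1 − d) + (1 − ρ)]/2

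Power = Φ(2.80/√R − 1.96), where 2.80 = 1.96 + 0.84. The number per arm cancels.

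For d = 0.20 and ρ = 0.3:

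- Both lost: R = 1/0.8 = 1.25, power 70.7%.
- Baseline kept: R = (1.3/0.8 + 0.7)/2 = 1.1625, power 73.8%.

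| Dropout d | Both lost | Baseline kept (ρ = 0.7 to 0.3) | Gain in points |
|---|---|---|---|
| 10% | 75.7% | 76.4–77.2% | 0.7–1.5 |
| 20% | 70.7% | 72.0–73.8% | 1.3–3.1 |
| 30% | 65.0% | 67.0–69.8% | 2.0–4.8 |

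Most of the power loss comes from the missing week-6 diary, which earlier collection of the first diary cannot restore.

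**The case against.** The strongest reply is that this is a small operational gap in two secondary outcomes, and that the plan is silent on earlier collection without forbidding it. Several parts of that reply stand.

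- A reader might infer that everyone who stops capsules loses their void data. The documents do not support this. Someone who stops but attends week 6 can hand in both diaries, and the tolerability survey at follow-up expects to hear from participants who discontinued. A withdrawing participant who returns capsules could also bring the diary, although the plan does not ask for it.
- A reader might infer that the timing of the diary can never be verified. Participants are given a log for the date and time of each dose, and a dated diary could be compared with it. The diary forms and the two-week phone script are appendices not shown, so whether they carry a date or capture counts is unknown. What can be said is that no described step makes the comparison.
- A reader might infer that the payment rule causes back-filling, or that seeing the first diary alters the second. Nothing in the documents shows either. A diary reconstructed from memory could err in either direction; only one recorded on treatment has a predictable effect. With blinding, there is no stated reason for the arms to differ in this.
- A reader might apply the loss of 5 of 40 (12.5%) from the multiple sclerosis pilot described in the background. That was a six-month study in another disease, and it counts dropouts. It does not measure the harm from late collection, because dropouts lack a week-6 diary in any case.

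These points narrow the concern but leave the week-2 instruction in conflict with the pre-treatment requirement, and they leave withdrawals without a diary request.

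**Conclusion.** The point holds in limited form. As written, the procedures collect the pre-treatment diary only at week 6, do not ask for it at withdrawal, and allow a missing one to be completed after dosing should have begun. The pre-treatment requirement and the two-week instruction contradict each other and must be reconciled.

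The effect is confined to secondary outcomes b and c; the primary ICSI and VAS baselines are unaffected. The main reason to act is the validity of the baseline. Dilution ranges from negligible (97.5% of the effect retained) to substantial (62.5%), depending on two shares that the documents do not give. The power argument is weak, at about 1–5 points over the assumed range. A further gain is that dropouts' baseline voids could be described and used in the mixed model. This is a cheap improvement to data collection, and it does not threaten the trial's main conclusion.

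**What to change.** 1. At the existing liver-result call, confirm that the diary already required before dosing is complete. Record its date and the day and night void counts, by read-back or photo.
2. Under Withdrawal criteria and the early-withdrawal procedures, ask for the diary along with the unused capsules.
3. Reword the two-week instruction in Follow-up Schedule and Study procedures so that it agrees with the pre-treatment requirement.
4. In Data Analysis, state that the diary date will be checked against the first logged dose, and that a diary dated after that dose will not be analysed as baseline.

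The cost is a few minutes on a call that already takes place, an occasional short delay for an unfinished diary, and small wording changes in the sections named. No dosing rule changes, because the plan already places the diary before the first capsule.
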